#### 5.2 Follow up visits

At each follow-up visit (see Figure 1 for the visit schedule), the physician documents the clinical examination findings (HECSI, FECSI, EASI, global disease severity (IGA)), the prescribed therapy including the rationale for the prescription, as well as reasons for changing or continuing therapy and possible adverse drug reactions (ADRs).

The patient questionnaire for follow-up visits is analogous to the questionnaire for baseline visits (see Table 2).

#### 5.3 Interim visits

Interim visits may take place between the regular study visits if the treating physician deems this necessary. Reasons for interim visits can be, for example, flares of the disease, the occurrence of ADRs due to the treatment of aH&FE, hospitalization due to aH&FE or a change in the anti-inflammatory systemic therapy.

The physicians' and patients' questionnaires for the interim visits correspond to those for the follow-up visits (see 5. 2, Table 2).

#### 5.4 Drop-out

Patients can withdraw from the study at any time at their own request and without giving reasons and without consequences for their future treatment.

#### 6 STUDY DOCUMENTATION / DATA MANAGEMENT

#### 6.1 Site signature log of recruitment sites

It is the responsibility of the investigator of the recruitment sites to ensure that the registry project is conducted in accordance with all legal requirements and the registry protocol and that data is documented correctly.

It must be ensured that all data collected as part of this registry study (including medical history, concomitant diseases, examination data, results of examinations and adverse events) is only collected by appropriately authorized persons. The authorization of these persons and their scope of authorization is carried out by the investigator of the recruitment site via an authorization list (Delegation Log/Site Signature Log), which is filed as an original in the registry study folder. Furthermore, it must be ensured that the signatures and abbreviations can be clearly assigned to the authorized persons.

#### 6.2 Patient identification log

Data collection is pseudonymized. The recruitment site notes the persons enrolled into the registry on a special patient identification list (Patient Identification Log). This must ensure a clear assignment of the participating person to the patient ID number in the registry.

The patient identification list must be treated confidentially and remains at the recruitment site. In addition, the participation of the person concerned in the registry must be noted in the patient file. In the physician and patient questionnaires, the data are entered in pseudonymous form. The registry head office receives pseudonymized data only.

#### 6.3 Recruitment site registry study file

For the registry study an Investigator Site File (ISF) is provided to the recruitment site by the registry head office. All documents required for the registry study are stored in this file. It contains the essential documents, such as the registry protocol, a sample of the patient information/consent form, the favourable assessment of the lead ethics committee, etc. Forms provided by the registry head office must be used.

The recruitment site is responsible for ensuring that the ISF is up-to-date and complete. This is checked as part of the monitoring process in accordance with the regulations.

After completion or cancellation of the study, the documents must be kept for 10 years.

#### 6.4 Data capture, data protection and data security

All clinical and patient-reported data are entered into an electronic data entry system specially developed for the ReaCT registry. A REDCap (Research Electronic Data Capture) database is used for this purpose. [27, 28]

REDCap is a secure, web-based software platform designed to support data capture for research studies, providing 1) an intuitive interface for validated data capture; 2) audit trails for tracking data manipulation and export procedures; 3) automated export procedures for seamless data downloads to common statistical packages; and 4) procedures for data integration and interoperability with external sources.

The physician enters clinical data browser-based on a PC or other terminal device. The corresponding questionnaire for the patient is opened on an iPad/mobile device using a QR-Code that is created from the physician's data-recording system. The patient enters their data webbased into the REDCap database using the iPad/mobile device. This ensures that the patient cannot view any data other than the questionnaire they are working on (neither their own previously entered data nor the physician's treatment data or data from other patients).

Data is primarily entered directly into this database. Alternatively, data can also be collected with a paper version of the questionnaires and later documented in the REDCap database if electronic data entry is not possible at the site.

The electronic data capture tool REDCap is hosted at the Koordinierungszentrum für klinische Studien Dresden (KKS). The KKS holds a REDCap-licence that can be used for the ReaCT registry on a contractual basis. The KKS is responsible for the management of the digital questionnaires as well as the administration of access authorizations for the involved study personnel of the recruitment sites. Moreover, the KKS also manages the corresponding server for data base storage, which is based in Dresden, Germany. The cooperation is based on a contract between the registry head office and the KKS. Mobile devices will be provided to all recruitment sites for the entry of patient questionnaires. The devices are the property of the Medical Faculty of the TU Dresden, whose IT division is responsible for the mobile device management. No data is stored on these devices. The pseudonymized data is transmitted to the REDCap database online via a browser-based web-application. Data transfer is encrypted. All data entry is tracked in the REDCap audit trail.

The physician ensures that all patient data is entered into the study documents immediately, legibly, completely, correctly and in accordance with the patient records. In case of incomplete or implausible data, the registry head office at ZEGV Dresden will contact the respective recruiting site.

The entries in the data collection system are immediately checked in REDCap for completeness and plausibility and, if necessary, corrected using automatic feedback or help instructions. The medical study personnel have an up-to-date view of all entries at all times and can

check them for completeness and quality. A final plausibility check is carried out after the database has been extracted to create a plausibility-checked data set. This is necessary to clarify discrepancies in the documentation of the course of therapy in addition to data completeness to obtain an analyzable data set. Any discrepancies are requested from the recruiting sites for clarification and correction.

In case of a termination of the registry study, the database is closed after all entries have been entered and any queries have been clarified. This process is documented.

#### Data protection and data security

In the database only pseudonymized data is collected. Clinical and patient-reported data is linked via a patient ID to an individual person. This is documented in the Patient Identification Log that is kept in the recruitment sites. Neither in the electronic database nor the paper and pencil version of the questionnaires patient-identifying data such as name, address or date of birth appear. It is therefore ensured that only pseudonymized data is collected.

If the electronic data entry system cannot be fully applied at a study site, it is possible to complete the physician and patient questionnaires using a paper-based version of the physician and patient questionnaires (paper and pencil). Data entry into the database is done by the study personnel later on. In case the recruitment site is not able to enter paper-based questionnaires by itself, the completed original pages (without names or initials) are sent to the registry head office at ZEGV Dresden, a copy remains at the recruitment site. After data entry and electronic storage of the paper questionnaires, the original questionnaire is returned to the recruitment site for storage in accordance with legal requirements.

#### 6.5 Description of measurement instruments

As detailed below, we follow the recommendation of the HOME initiative the use the core outcome instruments EASI, POEM, NRS 11 for intensity of itch, RECAP, and DLQI in all atopic dermatitis studies. [29] Whenever available, validated outcome measurement instruments are applied.

#### **HECSI and FECSI Scores** (see CRF physician, German)

The Hand Eczema Severity Index (HECSI) is used to measure the severity of hand eczema. The HECSI gives a total score from 0 to 360 points, based on assessments of the severity of six different morphological signs (erythema, infiltration/papulation, vesicles, fissures, scaling and edema) using a 4-point severity scale (0, no skin changes, to 3, severe disease), and the extent of eczema in five areas of the hands (fingertips, fingers (except fingertips), palms of hands, back of hands, wrists) by assessing the percentage of the regions these lesions occupy and converting it to a score based on a 5-point scale (the area score). For each of the hand regions, the region score will be calculated by adding up the severity scores for the 6 clinical signs of hand eczema and multiplying with the area score. The HECSI score equals the sum of the region scores. It is one of the most widely used measurement instruments for hand eczema severity and its reliability and validity has been studied in detail. HECSI was shown to pick up changes in hand eczema severity. HECSI severity grades are: clear = 0; almost clear = 1-16; moderate = 17-37; severe = 38-116; very severe ≥117. [16, 30, 31] The severity of foot eczema will be measured with the Foot Eczema Severity Index (FECSI), which has been created based on the HECSI for ReaCT.

#### Dermatology Life Quality Index (DLQI) (see CRF patients, German)

The DLQI is a validated questionnaire with content specific to those with dermatologic conditions. It consists of 10 items addressing the subject's perception of the impact of their skin disease on different aspects of their quality of life over the past week such as dermatology-related symptoms and feelings, daily activities, leisure, work or school, personal relationships, and the treatment. [32-34] The questionnaire records the QoL of the past 7 days. Each item is scored on a 4-point scale (0 = 'not at all /not relevant'; 1 = 'a little'; 2 = 'a lot'; 3 = 'very much'). The total score is the sum of the 10 items (score range from 0 to 30); with 0–1 = no effect at all on patient's life, 2–5 = small effect on patient's life, 6–10 = moderate effect on patient's life, 11–20 = very large effect on patient's life, and 21–30 = extremely large effect on patient's life. [35] A decrease in DLQI represents an improvement. The minimum clinically important difference for the DLQI is 4; a high score is indicative of a poor quality of life. [36] A validated German version is available. [33, 34, 37, 38]. The DLQI allows comparisons across studies of different dermatological diseases.

#### Hand Eczema Impact Scale (HEIS) (see CRF patients, German)

Health-related quality of life is widely used as a patient-reported outcome to evaluate clinical trials. The Hand Eczema Impact Scale (HEIS) (n=9 questions) is a validated disease-specific instrument used to assess health-related quality of life in patients with hand eczema according to the domains of (a) proximal daily activity limitations (PDAL), (b) embarrassment with appearance of the hands (Emb), (c) frustration with chronic hand eczema, (d) sleep, and (e) work. Improvements of  $\geq$  1.3 points in HEIS score and HEIS PDAL score represent clinically meaningful, important changes. Improvements of  $\geq$  1.5 points in HEIS Emb score represent clinically meaningful, important changes. A validated German version is available. [39]

## Assessment of global disease severity at hands and feet, respectively, by physician (IGA) and patient (PGA) (see CRF physicians/patients, German)

In addition to a complex, symptom-based score system such as the HECSI and QoL assessments, Held et al. recommend that a global, basic assessment of the severity of the disease or its change should always be made in studies. [40] An IGA (Investigator's Global Assessment) is a frequent target criterion in clinical studies. This register applies the HF (hand and foot) IGA, an assessment tool that distinguishes between five degrees of severity. [21] The severity grades from 0 (clear) to 4 (severe) are defined by the presence and intensity of certain skin changes. Severity is stepped down if the extent of lesions is limited and stepped up according to the severity of vesicles or fissures.

The PGA (Patient's Global Assessment) is a target criterion similar to the IGA, in which the patient himself makes the assessment. It distinguishes six degrees: clear, almost clear, mild, moderate, severe, and very severe. These categories are not defined by signs or symptoms and therefore provide an easy, subjective assessment from the patient's perspective.

## Work Productivity and Activity Impairment Questionnaire (WPAI) (see CRF patients, German)

The impact of aH&FE on the subject's ability to work and perform regular activities will be assessed by WPAI, which is an instrument to measure impairments in both paid work and activity impairment in leisure time. The WPAI consists of six items, and scores can be calculated for four domains, each reflecting the percentage impairment due to aH&FE during the past seven days, with higher numbers indicating greater impairment and less productivity.

The questions cover the characteristic areas of absenteeism and restricted productivity due to attendance at work with health problems (presenteeism). With regard to the areas of application, the WPAI can be used across all occupations and a variety of illnesses. A WPAI version

for chronic hand dermatitis in English has been validated (WPAI-ChHD); the discriminative and evaluative validity were established with the exception of work time missed (due to a low rate of absenteeism). [41] A German translation of the WPAI is available, and will be adapted to refer specifically to hand eczema and foot eczema, respectively, in accordance with the developers' recommendations. [42]

#### Patient-oriented eczema measure (POEM) (see CRF patients, German)

The Patient Oriented Eczema Measure (POEM) is a 7-item validated questionnaire used to assess disease symptoms in children and adults. [43] Patients evaluate frequency and severity signs and symptoms of AD during the past week: individual items of bleeding, oozing, cracked, flaking and dry/rough skin, and their impact on sleep on a 5-point scale. [43, 44] The maximum value of the POEM is 28 points. The POEM captures the symptoms relevant to patients and correlates well with the DLQI and PGA.

The original POEM questionnaire is adapted for ReaCT to refer to either hand eczema or foot eczema.

# Center for Epidemiological Studies Depression Scale (CES-D) (see CRF patients, German)

The CES-D scale is a scale to measure depressive symptomatology in the general population and is considered a useful tool for epidemiological studies on depression. The items of the scale are the symptoms associated with depression and have already been validated. [45]

#### Eczema Area Severity Index (EASI) (see CRF patients, German)

The EASI is a validated measure used in clinical practice and clinical trials to assess the severity and extent of AD. [46] The EASI is a composite index with scores ranging from 0 to 72. Four AD disease characteristics (erythema, thickness [induration, papulation, edema], scratching [excoriation], and lichenification) will each be assessed for severity on a scale of 0 (absent) through 3 (severe). In addition, the area of AD involvement will be assessed as a percentage by body area of head, trunk, upper limbs, and lower limbs, and converted to a score of 0 to 6. In each body region, the area is expressed as 0, 1 (1% to 9%), 2 (10% to 29%), 3 (30% to 49%), 4 (50% to 69%), 5 (70% to 89%), or 6 (90% to 100%). Higher values indicating more severe disease. [46-48] The particular benefit of the instrument lies in highlighting changes in the severity of the disease during the course of treatment. [27]

#### **RECap of AtoPic eczema (RECAP)** (see CRF patients, German)

Recap of atopic eczema (RECAP) is a patient-reported outcome measure assessing eczema control. The severity of atopic dermatitis in the past 7 days is recorded in seven dimensions

on a 5-point scale. [86-89] This instrument has been developed and validated in the UK. There are self-reported and proxy-reported versions in English, Dutch and German. [49] The HOME Initiative recommends the use of the RECAP as a core outcome instrument in all atopic dermatitis studies. [50]

The original RECAP questionnaire is adapted for ReaCT to refer to either hand eczema or foot eczema.

#### Numeric rating scales NRS itch and worst itch (see CRF patients, German)

The NRS itch is comprised of two items and represents the numbers 0 (no itch) to 10 (worst imaginable itch). Subjects are asked to rate the average intensity during the past 3 days and the worst intensity of their itch within the past 24h using this scale.

The itch caused by hand eczema and foot eczema is rated separately.

#### Sleep Disturbance Numerical Rating Scale (SD NRS) (see CRF patients, German)

The SD NRS is measuring sleep loss during the past 3 days and comprises of one item. It represents the numbers 0 (no sleep impairment) to 10 (unbearable sleep impairment). SDs caused by hand eczema and foot eczema are rated separately.

#### 6.6 Adverse drug reactions (ADR) and pharmacovigilance regulations

The registry also records adverse drug reactions that occur during the use of new system therapies. The aim is to gather information on the safety of authorized therapies in routine care.

Definition: Adverse drug reactions (ADRs) are harmful and unintended reactions to medicinal products intended for use in humans. Adverse drug reactions therefore mean that a causal relationship between the medicinal product and the event that has occurred cannot at least be ruled out. Adverse drug reactions are generally independent of the intended use of the medicinal product. The definition of the term therefore includes the consequences of e. g. overdose, misuse, abuse, misapplication, improper use or application errors, as well as use during pregnancy and breastfeeding.

Adverse drug reactions (ADRs) from the treatment of aH&FE are recorded and documented in a standardized manner in accordance with the applicable legal requirements if suspected by the physician and/or patient.

The type of ADR (sign, symptom or disease, preferably diagnoses), start and end of occurrence, intensity (mild = easily tolerated, moderate = affects daily activities, severe = daily activities/work not possible), suspected connection with current system therapy of the aH&FE,

measures or actions to restore or improve the well-being of the person concerned and outcome of the event are recorded.

The reporting process is illustrated in Figure 2. Physicians participating in the registry report ADRs occurring in routine care that are suspected to be related to a product of a pharmaceutical company that supports the registry to the principal investigator without personal reference (pseudonymized).

The study director forwards this report to the pharmacovigilance contact of the pharmaceutical company concerned, provided this has been contractually agreed. The participating physicians agree to make the results of additional examinations that serve to confirm the diagnosis of ADRs (e. g. autopsy findings, hospital reports, consultation reports, etc.) accessible in a suitable manner without personal reference (pseudonymized). The study director will establish the relevant contact between the pharmacovigilance department of the pharmaceutical company concerned and the reporting physician. A list of products relevant for ADR reporting will be made available to the participating physicians by the study management.

[figure not shown]

Figure 1: Pharmacovigilance Process

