#### 4.3 Endpoints

#### **Primary Endpoints**

In analogy to the recommendations of the HOME initiative, we consider changes in the following primary endpoints for real-world efficacy of applied therapies:

- Objective severity of clinical signs, in ReaCT measured with HECSI-50, HECSI-75, and HECSI-90 six months after treatment was first prescribed (analogue analyses concerning FECSI)
- Patient-reported symptoms measured with POEM six months after treatment was first prescribed
- Disease control over time measured with RECAP six months after treatment was first prescribed
- Quality of life measured with HEIS six months after treatment was first prescribed
- Another primary endpoint is the safety of applied treatments at each visit.

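### The ADR record in section 6.6 does not capture medical seriousness and has no causality item for a drug already stopped, although safety is a primary endpoint

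*Protocol*

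**What the plan says.** Section 6.6 lists six kinds of information for each ADR. It begins with "The type of ADR (sign, symptom or disease, preferably diagnoses), start and end of occurrence", continues with "intensity (mild = easily tolerated, moderate = affects daily activities, severe = daily activities/work not possible), suspected connection with current system therapy", and closes with "measures or actions to restore or improve the well-being of the person concerned and outcome of the event are recorded". No item for seriousness is listed.

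The same section describes its scope in different ways. Its first sentence reads: "The registry also records adverse drug reactions that occur during the use of new system therapies". A later paragraph is wider: "Adverse drug reactions (ADRs) from the treatment of aH&FE are recorded and documented in a standardized manner in accordance with the applicable legal requirements". The causality item then refers to the current systemic therapy only. A separate reporting route covers "ADRs occurring in routine care that are suspected to be related to a product of a pharmaceutical company that supports the registry".

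Section 4.3 gives these data high standing: "Another primary endpoint is the safety of applied treatments at each visit". Section 5.3 names among the reasons for an optional interim visit "the occurrence of ADRs due to the treatment of aH&FE, hospitalization due to aH&FE or a change in the anti-inflammatory systemic therapy".

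**The concern.** Safety data are usually read along two axes: how medically important a reaction was, and which drug is suspected. The item list in 6.6 is weak on both.

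On importance, the grade measures disruption of daily life. That is a legitimate thing to record, but it is a different quantity from seriousness, and nothing in the list records seriousness directly.

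On attribution, this registry follows patients through sequences of systemic drugs. The synopsis makes treatment sequence, drug survival and change of treatment part of a primary objective. ADRs around a change of drug are therefore among the most informative, and they are the ones for which the word *current* is least clear.

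What is at stake is data collection, not analysis. A statistical analysis plan can choose how to summarise recorded fields, but it cannot recreate a seriousness judgement or a physician's suspicion about an earlier drug that was never entered.

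**Working it through.** No arithmetic applies. The check sets the sections of the protocol side by side.

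1. **Items fixed in 6.6.** Type, start and end, intensity, suspected connection with the current systemic therapy, measures, outcome. Table 1 (physician case report form) has no ADR row that adds to this list.

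2. **What the intensity scale can express.** Moderate and severe are both defined by effect on daily activities or work. A reaction without such effect meets neither definition, whatever its medical importance. Mild is defined by tolerability. For a symptom-free abnormal laboratory finding the scale gives no guidance, and the type item names signs, symptoms and diseases without naming laboratory findings. Such a reaction might be graded mild, left without a fitting grade, entered as a diagnosis, or not recorded. In none of these cases does the grade carry its importance. Conversely, a short self-limited symptom that keeps a patient from work meets the definition of severe.

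3. **Whether another item supplies importance.**
   - Measures and outcome carry some information. Measures are described as steps for the patient's well-being, not explicitly as what was done with the drug.
   - Section 5.2 documents reasons for changing or continuing therapy, but states no link from that reason to an individual ADR.
   - Section 5.3 mentions hospital admission, but for the eczema, not for a reaction.
   - Hospital and autopsy reports appear in 6.6 only within the reporting route for products of supporting companies. Supplementary evidence of importance may therefore differ between drugs.

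4. **Scope wordings in 6.6.** First sentence: new systemic therapies. Later paragraph: treatment of aH&FE in general, which on its words is not limited to new, current or even systemic treatment. Causality item: current systemic therapy. The three do not coincide.

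5. **Situations in which *current* does not fit.**
   - *At a switch.* Section 5.2 has the physician document the prescribed therapy, the reasons for change and ADRs at the same visit. Whether *current* then means the drug being stopped or the drug being started is not defined.
   - *After stopping without replacement.* There is no current systemic drug to link to. Regular visits may be 6 months apart (section 5), and interim visits are optional (section 5.3).
   - *At baseline.* Section 4.2 admits patients whose systemic therapy took place within the past 24 months, and section 5.1 records possible ADRs at the baseline visit. A reaction to a drug that ended before inclusion has no stated link.

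6. **What can be reconstructed later.** ADR dates set against the therapy documentation show whether a reaction began before or after a change. Timing does not record which drug the physician suspected. The suspected-product route covers supporting companies' products only, so it does not close the gap for the other drugs.

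**The case against.** The strongest reply is that 6.6 is a short summary of a form that is not shown, that documentation follows the applicable legal requirements, and that the pharmacovigilance figure is missing from the available text. A seriousness box or a named suspected drug may exist on the form. That stands as a limit: if so, only the wording of 6.6 needs to change.

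A second reply is that a functional scale is an ordinary design choice and that the analyses are descriptive and exploratory. This also stands in part. The scale need not be replaced, and how safety is summarised can be left to the analysis plan. It does not answer the absence of a seriousness item beside the scale.

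Safeguards also exist. Reasons for change, measures, outcome and dates are recorded. Both an ADR and a switch can prompt an interim visit. Visits after a new systemic drug fall at 4 weeks, 3 months and 6 months, so the 6-month gap does not describe the time just after a switch. Section 6.4 provides a final plausibility check of the course of therapy, with queries to sites. These reduce the loss without removing it.

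Three stronger readings are tempting and are not supported:

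- *Every symptom-free laboratory reaction is graded mild.* Mild means easily tolerated, and the scale is silent on laboratory findings, so no fixed share follows.
- *Reactions are shifted from the stopped drug to its replacement.* A physician who suspects the old drug need not affirm a connection with the new one, and *current* could be read as current at onset. The old-drug link lacks a stated item; it is not reassigned.
- *Drugs will be ranked wrongly on safety.* The protocol ranks no drugs by ADR intensity.

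**Conclusion.** The point holds in limited form. As written, section 6.6 cannot reliably separate medically serious from non-serious ADRs, and it provides no causality item for a systemic drug already stopped. Its three scope wordings are inconsistent with one another. Because safety is a primary endpoint and unrecorded fields cannot be restored later, this should be corrected.

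The size cannot be given as a number. The protocol states no ADR rates, no switching rates and no share of ADRs without functional impact, and any figure for misattributed reactions would rest on invented shares. The affected records can only be described by kind: medically important reactions without effect on daily activities or work, and reactions suspected to come from a drug that ended at a switch, without replacement, or before baseline.

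The conclusion assumes that the item list in 6.6 reflects what the form collects.

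**What to change.** In the item list of section 6.6 and in the ADR form:

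- Keep intensity, and add beside it seriousness (yes/no, with the standard criteria) and the action taken with the suspected drug.
- Replace the reference to current systemic therapy with the named suspected systemic aH&FE drug or drugs, including any stopped since the previous visit or before baseline, with start and stop dates if not already held.
- Reconcile the three scope wordings, so that the opening sentence, the recording paragraph and the causality item cover the same treatments.

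The cost is a few REDCap fields, a protocol wording change and a slightly longer form. ADRs recorded before the change will lack the new fields unless sites are queried. If the form already contains them, the change is limited to aligning the text of 6.6.
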